5.2 Cohort 1—Surgery Arm

In Cohort 1, 15-20 eligible participants who require reoperation will be treated with abemaciclib for 10-14 days prior to surgery. The last dose should be on the day of surgery and taken 1-3 hours prior to surgery and tumor removal. Since participants in cohort 1 are undergoing PK testing, accurately recording the time of study drug administration on day of surgery and recording the time of tumor removal are especially important and required.

In general, pre-operative, operative, and post-operative evaluations will consist of standard clinical practice. Required evaluations and research samples are detailed in Section 10.

After surgery on study, cohort 1 participants will come off study treatment and pursue standard cancer treatments as per the treating physician's discretion. Participants who enrolled on the surgical cohort before the surgical cohort was converted into a Phase 0, who have already started post-surgical abemaciclib dosing, and are benefitting from post-surgical abemaciclib treatment may remain on abemaciclib at the discretion of their treating physician and the approval of the overall PI, [name]. These patients should instead follow the Study Calendar intended for Cohort 2 (nonsurgical) patients and their post-surgical C1D1 will represent C1D1 on the Cohort 2 study calendar.

Following registration, Cohort 1 pre-surgical Day 1 subjects should be evaluated for eligibility to treat based upon dose modification criteria outlined in Table 6.3 and not General Eligibility Criteria outlined here in Protocol Section 3; General Eligibility Criteria outlined here in Protocol Section 3 need only be met during screening for trial.

The goal is to have 15 eligible patients with adequate tissue for assessment of the primary objectives for this cohort. If sufficient tissue is not obtained for a patient enrolled in this cohort, the patient should continue treatment as originally intended and the clinical results reported. However, additional patients will be added to the cohort for the purpose of meeting the objectives related to tissue analysis. A maximum of 20 patients may be enrolled in this cohort. If the number of patients required to be replaced exceeds 5 consideration will be given to stopping enrollment to this cohort based on lack of feasibility.

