9.2 Laboratory Correlative Studies

Correlative studies and tissue required for these are mandatory for all participants with the exception of specified imaging studies.

Correlative study time points are included in Section 10 (Required Activity Calendar).

NOTE: Study Sponsor, or his/her designee, may ultimately opt to not pursue analysis of one or more of the correlative studies specified in the protocol if the study is not positive and/or the data gained from the analysis is no longer believed to be helpful.

Cohort 1: In this cohort, patients with recurrent GBM will receive drug for 10-14 days prior surgery, abemaciclib should be taken as close to a 7AM – 7PM schedule as possible during pre-

surgery cycle. The last dose should be on the day of surgery 1-3 hours prior to surgery and tumor removal.

During surgery, tumor tissue and plasma will be collected simultaneously. Planned analyses for resected tumor tissue as follows:

- 1) Frozen tumor samples and plasma samples will be evaluated for drug concentration using liquid chromatography tandem mass spectrometry (LC-MS/MS) to derive a tumor/plasma ratio. Tumor concentration will be compared to plasma drug concentrations to determine if therapeutic levels of abemaciclib can be achieved in both enhancing and non-enhancing tumor.
- 2) Frozen tumor samples, archival and study surgery FFPE tumor tissue will be evaluated for drug target pathway dysfunction and for pharmacodynamic alterations of signal transduction molecules relevant to the response to abemaciclib. Tumor tissue will be analyzed by IHC and proteomics studies for pRb (S807/811), proliferation (e.g. Ki-67), and apoptosis (e.g. cleaved caspase 3) to determine if abemaciclib can achieve a pharmacodynamic effect in enhancing and non-enhancing tumor tissue. These data will be compared to similar analyses performed on tumor tissue not exposed to abemaciclib obtained from each participant's prior surgery, and from tumor specimens from untreated glioblastoma patients who undergo reoperation as part of another ongoing study (ABTC 1301: MLN0128 in recurrent glioblastoma).
- 3) Fresh-preserved tumor tissue and/or whole blood will be evaluated for the drug's immunostimulatory effects based on the following immunological assays:

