Tissue PK ([name], OSU)	Cohort 1	Liquid chromatography - tandem mass spectrometry (LC- MS/MS)	Fresh frozen tissue from protocol surgery (enhancing and non- enhancing tumor)	Protocol surgery: 200mg of fresh frozen tissue from the contrast-enhancing tumor placed into individual cryovial labeled 1 (CE-PK). If deemed medically safe and feasible, 200mg of fresh tissue from non-contrast-enhancing tumor and placed into individual cryovial labeled 3 (NCE-PK).	The OSUCCC Pharmacoanalytical Shared Resource Attn: [name] [name] [contact] [contact] Email: [contact]
Plasma PK ([name], OSU)	Cohort 1	Liquid chromatography - tandem mass spectrometry (LC- MS/MS)	Peripheral blood (pre-treatment, D8, at tumor resection)	4mL blood should be collected (EDTA) prior to start of pre-surgery drug Day 1 (pre-dose), pre-surgery Day 8 (pre-dose), and on day of surgery at time of tumor resection. Plasma should be separated and collected in a cryotube (polypropylene cryovials Nunc) that can be snap frozen. Plasma PK cryotubes should be labeled with date drawn, time drawn, participant number & initials, and PK time point, then frozen at -70°C or below	The OSUCCC Pharmacoanalytical Shared Resource Attn: [name] [name] [contact] [contact] Email: [contact]
Plasma PK ([name], OSU)	Cohort 2	Liquid chromatography - tandem mass spectrometry (LC- MS/MS)	Peripheral blood	4mL blood should be collected (EDTA) predose at C1D1, C2D1, C3D1 and C4D1. Plasma should be separated and collected in a cryotube (polypropylene cryovials Nunc) that can be snap frozen. Plasma PK cryotubes should be labeled with date drawn, time drawn, participant number & initials, and PK time point, then frozen at -70°C or below	The OSUCCC Pharmacoanalytical Shared Resource Attn: [name] [name] [contact] [contact] Email: [contact]

T' DD HIG	G 1 :	HIGC DI	A 1' 1PPPP '	A 1: 100 (: 1 1 1:1 :	D WHILE (# ALLED LODG)
Tissue PD IHC,	Cohort	IHC for pRb	Archived FFPE tissue	Archived: 20 unstained plus slides cut at 5um	[name] (attn.: Adult Path CRC)
Proteomics, and	1	(S807/811),	and fresh frozen	thickness	Dana-Farber Cancer Institute
Tumor		proliferation, and	tissue from protocol	Protocol surgery: 10 unstained slides cut at 5um	Center for Molecular Oncologic Pathology -
microenvironment		apoptosis	surgery	thickness	JF215B

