Ten Green top tubes (each 10ml/tube – sodium heparin tubes preferred) should be collected prior to the start of pre-surgery Day 1 (pre-dose) and prior to morning abemaciclib dose on day of surgery. Blood samples for immunologic assays should be shipped (along with the fresh-preserved tumor tissue) via FedEX for overnight delivery directly to UCLA as described in Table 9.2.

Cohorts 1 & 2 Plasma Pharmacokinetic (PK) Samples:

Cohort 1 Pre-Surgery/Surgery

4mL blood should be collected in purple-top EDTA vacutainer (Becton Dickinson Catalog # 367861 or 367844, Franklin Lakes, NJ) prior to start of pre-surgery Day 1 (pre-dose), pre-surgery Day 8 (pre-dose), and on day of surgery at time of tumor resection. All samples should be prior to morning abemaciclib dose.

Cohort 2

For all Cohort 2 participants, 4mL blood should be collected (in purple-top EDTA vacutainer (Becton Dickinson Catalog # 367861 or 367844, Franklin Lakes, NJ) at C1D1 (pre-treatment), C2D1, C3D1 and C4D1(if a participant comes off study treatment prior to C4D1 visit, then an end of treatment sample should be drawn). All samples should be prior to morning abemaciclib dose.

Handling of Specimen(s)

- Obtain venous blood by standard phlebotomy technique from a peripheral access point. NOTE: Suggest using a minimum 18G needle to avoid sample hemolysis.
- Fill-up the tubes as much as possible until blood flow stops.
- GENTLY invert each tube several times (8-10 times) immediately after collection to avoid sample hemolysis.
- Place samples immediately **on ice** after collection; samples must be processed **within 20 minutes**.

Processing instructions

- 1. Invert sample 8-10 times immediately before processing.
- 2. Place the sample(s) on ice or in a refrigerator and separate the **plasma within 60** minutes of collection at 1,500 2,000 x g for 10 minutes in swinging bucket (SW) or 15 minutes in a fixed angel (FA) rotor at 4°C in a refrigerated centrifuge. Make sure that the centrifuge reaches speed and is maintained throughout the entire spin.
- 3. Carefully remove tube from centrifuge.
- 4. Using a pipette, transfer equal aliquots of plasma into 2 labeled 2 mL cryovials, not exceeding 1.5 mL per cryovial.
- 5. Label samples as Abemaciclib PK, including protocol number (16-383), unique patient ID (assigned by the consortium), initials, date of collection, draw time, and time point.
- 6. Store plasma samples at -70°C or below until shipment or transfer to OSU.

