- o. Biochemistry albumin, alkaline phosphatase (ALP), bicarbonate (HCO₃), BUN, calcium, chloride, creatinine, glucose, magnesium, phosphorous, potassium, SGOT (AST), SGPT (ALT), sodium, total protein, total bilirubin, amylase and lipase, LDH and uric acid. If total bilirubin is greater than the upper limit of normal, direct and indirect bilirubin should be performed.
 - Coagulation assays of PT/INR, PT, PTT required at screening only.
- p. Archival tumor tissue per eligibility point 3.1.11 must be submitted to the DFCI Coordinating Center within 60 days of registration.
- q. Required at pre surgery C1D1 (pre-dose) and prior to the morning dose on the day of surgery.
- r. Required at pre surgery C1D1 (pre-dose), pre-surgery Day 8 (pre-dose), and day of surgery at the time of tumor resection for Cohort 1 participants.
- s. See section 9 for details on tumor tissue requirements. On-study surgery tissue should be submitted within 60 days of date of surgery.
- t. Please see protocol section 8.1.8 for abemaciclib administration instructions

Table 10.2 Required Activity Calendar for Cohort 2 only

Examination	Screening ^a	Су	cle 1	Subsequent Cycles	End of	30-day post	Long Term
	oci cerming	D1 ^b	D15 ^C	D1 ^d	тх ^е	drug ^f Fo	Follow Up ^g
Informed Consent ^h	Х						
Background Information	Х						
Inclusion/Exclusion Criteria ⁱ	Х						
Serum Pregnancy Test ^j	Х	Х		Х			
Vital Signs ^k	Х	Х	Х	Х	Х		
Neuro & Physical Exam	Х	Х	Х	Х	Х		
KPS	Х	Х	Х	Х	Х	Х	
Con-Med & Adverse Event				X			
Assessments ^m				A			
12-lead ECG	χn			χn			
Imaging – MRI ^O	χр	χр		Xo	Х		
Response Assessment ^q				Х	Х		
Hematology ^r	Х	Х	х	Х	х		
Serum Chemistry ^S	Х	Х	Х	Х	Х		
Coagulation (PT/INR, PT, PTT)	Х						
Submission of Archival Tissue	χ ^t						χw
Plasma PK Collection ^U		Х		Х			
Abemaciclib Administration ^V		Every 12 hours		Every 12 hours			
Follow-Up Info							Х

- a. To be performed within 14 days of registration unless specified otherwise.
- b. To be performed within 3 days prior to drug day 1 unless specified otherwise.
- c. Cycle 1, Day 15 visit has a +/- 2 days window.
- d. Within 3 days prior to day 1 drug, except imaging which is within 7 days prior to day 1 drug. Results of all assessments (aside from correlative studies) must be reviewed prior to taking drug for respective cycle.

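### Section 9.2 times the Cohort 1 surgery-day plasma PK sample both at tumor resection and before the morning dose; both cannot hold, and a pre-dose sample would normally overstate the tumor/plasma ratio

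*Combined protocol and SAP*

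**What the plan says.** The detailed collection instruction for Cohort 1 plasma PK samples in Section 9.2 lists three tubes: pre-surgery Day 1, pre-surgery Day 8, and one "on day of surgery at time of tumor resection. All samples should be prior to morning abemaciclib dose". The second sentence of that quote covers all three.

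On dose timing, Section 5.2 states: "The last dose should be on the day of surgery and taken 1-3 hours prior to surgery and tumor removal". Section 8.1.8, the Cohort 1 introduction in Section 9.2 and footnote d of Table 10.1 give the same 1-3 h interval, and footnote d says the dose is taken that morning. Appendix F allows no dose after surgery.

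On the intended pairing, Section 9.2 says: "During surgery, tumor tissue and plasma will be collected simultaneously". Table 9.2 times the Cohort 1 plasma PK tubes "prior to start of pre-surgery drug Day 1 (pre-dose), pre-surgery Day 8 (pre-dose), and on day of surgery at time of tumor resection", and footnote r of Table 10.1 reads: "Required at pre surgery C1D1 (pre-dose), pre-surgery Day 8 (pre-dose), and day of surgery at the time of tumor resection for Cohort 1 participants".

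A separate set of surgery-day tubes, for immunophenotyping, is meant to be pre-dose. Section 9.2 asks for them "prior to the start of pre-surgery Day 1 (pre-dose) and prior to morning abemaciclib dose on day of surgery", and footnote q of Table 10.1 agrees: "Required at pre surgery C1D1 (pre-dose) and prior to the morning dose on the day of surgery".

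On use of the data, Section 9.2 states: "Tumor concentration will be compared to plasma drug concentrations to determine if therapeutic levels of abemaciclib can be achieved". Section 13.1 plans one brain-to-plasma ratio per participant from a paired sample, and Section 13.4 reports tumor-to-plasma ratios descriptively.

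**The concern.** The two adjoining sentences in Section 9.2 give incompatible times for one tube. The wrong one is easy to follow in practice. Staff are already drawing the immunophenotyping tubes before the morning dose on the day of surgery, and the sentence covering all samples places the PK tube at that same draw. Section 8.1.8 pulls the same way, because on PK sampling days it holds the morning dose until after the clinic visit, before giving its own surgery-day instruction.

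A PK tube filled at the pre-dose draw holds trough plasma, while the tumor is removed after a further dose. The denominator of the ratio would then normally be too low. If some sites follow one sentence and some the other, the ratios also differ systematically between sites, in a cohort with a goal of 15 participants with adequate tissue and a maximum of 20.

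**Working it through.** **Consistency check**

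1. The tube is drawn at resection (Section 9.2, Table 9.2, Table 10.1 footnote r).
2. The morning dose is taken 1-3 h before surgery and tumor removal (Sections 5.2, 8.1.8 and 9.2; Table 10.1 footnote d), so the tube in step 1 is post-dose.
3. The sentence covering all samples makes the same tube pre-dose. With no dose after surgery (Appendix F), there is no later dose that a resection tube could precede.

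Steps 1 and 3 are incompatible. Table 9.2 and footnote r attach the pre-dose condition only to Day 1 and Day 8. The same sentence closes the Cohort 2 paragraph, where it fits. The pre-dose rule for the surgery-day PK tube has no support elsewhere in the PK sampling instructions.

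**Direction and size**

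The plan gives no figure to reproduce. Inputs from the documents are dosing every 12 h (Section 5.1), a terminal half-life of 17-38 h, apparent clearance of 38.3 L/h and apparent volume of 1300 L (Section 2.2). The last two imply a half-life of ln 2 × 1300 / 38.3 = 23.5 h, inside the stated range. Absorption rate (ka) and lag are not given; I assume ka of 0.1, 0.2, 0.5, 1.0 and 1.5 per hour and lags of 0, 1 and 2 h.

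For a one-compartment oral model at steady state without lag, with ke = ln 2 / half-life and τ = 12 h, plasma at time t after a dose is proportional to

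C(t) = exp(−ke·t) / (1 − exp(−ke·τ)) − exp(−ka·t) / (1 − exp(−ka·τ)).

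The pre-dose value is C(τ). For the same tumor sample, C(t)/C(τ) is the factor by which a pre-dose tube multiplies the ratio. A lag shifts the curve to the right.

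Worked example: half-life 23.5 h, ka 1.0 per hour, no lag, t = 2 h. Then ke = 0.0295; C(2) = 3.163 − 0.135 = 3.027; C(12) = 2.355; factor = 3.027 / 2.355 = 1.29.

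Without lag, over t = 1-3 h and all assumed ka:

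| Half-life | Factor |
|---|---|
| 17 h | 1.03-1.47 |
| 23.5 h | 1.02-1.32 |
| 38 h | 1.01-1.19 |
| Overall | 1.01-1.47 |

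With lag, over all three half-lives and all assumed ka:

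| Lag | t = 1 h | t = 2 h | t = 3 h |
|---|---|---|---|
| 1 h | 0.96-0.99 | 1.00-1.37 | 1.01-1.41 |
| 2 h | 0.96-0.99 | 0.92-0.98 | 0.99-1.31 |

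Steady state is a fair assumption after the minimum 10 days (240 h) of dosing: 1 − 2^(−240/38) = 98.7% at the longest half-life and more than 99.9% at the shortest.

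**The case against.** The strongest reply is that the intended timing is already clear. The sentence before the pre-dose rule names resection, and the simultaneous-collection statement, Table 9.2 and footnote r all agree. The pre-dose sentence looks like wording carried over from the Cohort 2 paragraph, and many sites would probably collect correctly. Dose, tumor-removal and draw times are all recorded, so a mistimed tube can be identified. The ratio is descriptive and feeds no decision rule. All of this stands. It limits the severity, but it does not remove a literal instruction that a site can follow in the detailed collection text.

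A second reply is that direction and size depend on absorption inputs the documents do not give, and that a 2 h lag would understate the ratio over most of the 1-3 h window. That is correct. Overstatement is the usual result in the scenarios run, not a certainty; the mismatch between trough plasma and post-dose tumor is present either way.

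A third reply is that the PK-day sentence in Section 8.1.8 speaks of a clinic visit, which surgery is not, and that the surgery-day sentence works as its exception. That reading is reasonable, but the text does not state it, and the surgery-day draw is itself a PK sample.

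**Conclusion.** The concern holds: the two sentences in Section 9.2 cannot both be followed for the surgery-day PK tube, and the rest of the protocol shows that resection is meant. If the pre-dose sentence were followed, the tumor/plasma ratio would be overstated by about 1-47% under the no-lag assumptions (about 2-32% at a 23.5 h half-life). A long enough absorption lag would reverse this, to an understatement of at most about 8%. These figures rest on a one-compartment model and assumed absorption.

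The plan gives no variability for the ratio, so how visible such a shift would be in about 15 pairs cannot be judged. The measured tumor concentration, which is the Cohort 1 primary objective in Section 1.2.1, and all decision rules are unaffected. The documents do not show that any tube was mistimed. This should be corrected, but it does not threaten the trial's main conclusions.

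**What to change.** - In Section 9.2, restrict the pre-dose condition to the Day 1 and Day 8 Cohort 1 PK samples and keep the surgery-day PK tube at tumor resection, matching Table 9.2 and footnote r. Leave the surgery-day immunophenotyping tubes pre-dose.
- In Section 8.1.8, reconcile the sentence on PK sampling days with the surgery-day sentence that follows it.
- Before computing any ratio, compare the draw time on each surgery-day PK tube with the recorded dose and tumor-removal times. Use only plasma drawn at resection as the denominator, and report any pre-dose surgery-day plasma separately. Such samples, entered at their actual times, could still inform the time-course modeling in Section 13.1.

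The cost is one sentence, one reconciliation and a check of times the protocol already requires to be recorded. The check also works if collection has finished. The downside is that any mistimed pair leaves the ratio analysis, which reduces an already small number of usable pairs.
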